8.1.3 Detection of a clinical meaningful result

Given the challenges of carrying out definitive randomised controlled trials in the rare disease setting, data from small scale studies have been highly influential in driving treatment advances. The global adoption of pembrolizumab for GTN is a case in point. Our initial observation was exceptionally high pembrolizumab efficacy amongst a series of 4 patients. These data were sufficient to result in a change in NHS guidelines to support funding of this agent for patients with resistant disease. As we and the global community have accrued more data, use of pembrolizumab is now recommended in global GTN management guidelines.

While, as per recommendations for feasibility studies, we did not conduct sample size calculations for the pembrolizumab vs control comparison, we note that even with such a small sample size we would have adequate power to detect a clinically significant difference between the arms. Second evacuation for disease recurrence has a complete response (CR) rate of ~25% based on a study done at our centre. Amongst the remainder who relapse, we estimate a 75% CR rate to pembrolizumab based on multicentre data on patients with drug resistant, metastatic disease. We thus estimate the CR rate of neoadjuvant pembrolizumab to be 81% ($100*[0.25+(1-0.25)*0.75]$). For 80% power with α of 0.05, 9 patients per arm are required. This is consistent with 20 patients in total, randomised 1:1 to the control and neoadjuvant pembrolizumab arms.

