From a translational research perspective, the unique immune biology of GTN offers an ideal opportunity to deepen our understanding of immune regulation in cancer. GTN arises from placental trophoblasts and as such is a semi- or fully allogeneic transplant with both maternal and paternal genomic contribution⁷. Conventionally, such HLA mismatched transplants are expected to be rapidly rejected by the host immune system that recognises paternal antigens as foreign, yet GTN can be widely metastatic and fatal without therapy. In parallel, the exceptionally high response rate of this disease to immunotherapy offers an opportunity to study the biology of an optimally activated anti-cancer immune response. Thus, GTN represents a model to

study both mechanisms of extreme immune evasion in a highly antigenic environment and the basis of immunotherapy sensitivity.

Here, we propose a feasibility window study of neoadjuvant pembrolizumab vs. no treatment prior to second evacuation of intrauterine postmolar GTN. The trial will enable us to determine whether pembrolizumab prior to second evacuation is acceptable to patients and feasible to deliver. This could directly set a new standard of care or motivate a larger, definitive study. Second evacuation tissues and blood samples will be used to support a CRUK funded study of immune regulation in cancer using GTN as a model, expected to yield novel insights into why the immune response is incapable of rejecting cancers in general and how pembrolizumab overcomes this. These insights will help develop new treatments and approaches to personalised care across cancer types.

1.2 Clinical Rationale: Reducing exposure to chemotherapy amongst patients with low-risk disease

Two broad treatment options are considered for patients with postmolar GTN that has not spread beyond the uterus and who otherwise are considered low risk according to FIGO international criteria⁸. Firstly, further evacuation of intrauterine disease and secondly systemic treatment with chemotherapy. Whilst further treatments may be required, the overall cure rate approaches 100%, thus it is desirable to offer the least toxic approach upfront.

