1.2.3 Immunotherapy before second evacuation may greatly enhance cure rates

T cells of the immune system can recognise and control tumours, but their function is limited by inhibitory receptors (checkpoints). Monoclonal antibodies directed against these receptors (checkpoint blockade immunotherapy [CPI]) have proven to be effective across cancer types^{23–25}. We have recently shown that GTN is profoundly CPI sensitive. Complete responses occur in ~70% of anti-PD1 treated patients⁴, the highest rate across all human cancers.

Whilst CPI is mostly utilised in the setting of advanced, metastatic disease, it is increasingly studied in other settings. Several studies have now shown that neoadjuvant immunotherapy prior to cancer resection is a powerful approach, resulting in complete pathological responses amongst patients with melanoma⁶ and lung cancer⁵ amongst other cancer types. Given that the efficacy of anti-PD1 therapy is higher in GTN than these other tumour types that are conventionally considered to be most immunotherapy response, we hypothesise that neoadjuvant pembrolizumab prior to second evacuation could significantly enhance the cure rate over second evacuation alone.

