8.1.2 Feasibility of recruitment

Estimated cure rate with second evacuation alone is approximately 25% in our cohort³. The cure rate with single agent chemotherapy is approximately 66%. Therefore under conservative assumptions, in order to demonstrate a clinically significant benefit of pembrolizumab prior to second evacuation of 66% cure vs. second evacuation alone (25% cure), 40 patients in total are required (80% power, significance level 0.05). To justify a larger study, this cohort would be recruited in no more than 3 years (14 patients/year).

Based on current caseloads, we estimate approximately 50 patients per year in the UK are eligible for the study, of whom 30 are managed at CXH. With 30 eligible patients, assuming 66% (n=20) are recruited in 1 year, the 95% confidence interval

is 50 – 84%. This is consistent with the recruitment target of at least 15 patients per year at CXH (30 patients/year x 0.5 [lower bound of the 95% confidence interval for the recruitment rate]). Thus recruitment of 20 patients in 1 year would give us confidence that a definitive study would be feasible.

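### Protocol 8.1.3 claims adequate power at 20 patients for a clinically significant difference, but shows it only for a projected 81% vs 25%; for the 66% vs 25% that 8.1.2 calls clinically significant, power is about 26% to 52%

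*Protocol*

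**What the plan says.** Section 8.1.2 takes second evacuation alone as the control: "Estimated cure rate with second evacuation alone is approximately 25% in our cohort". It then sizes a possible larger study. Under assumptions it calls conservative, and "in order to demonstrate a clinically significant benefit of pembrolizumab prior to second evacuation of 66% cure vs. second evacuation alone (25% cure"), it states that "40 patients in total are required (80% power, significance level 0.05").

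Section 8.1.3 first notes that no sample size calculation was made for the between-arm comparison, as is usual for feasibility studies. It then adds that "even with such a small sample size we would have adequate power to detect a clinically significant difference between the arms". The control rate is the same: "Second evacuation for disease recurrence has a complete response (CR) rate of ~25% based on a study done at our centre". The treated rate is new. It credits a 75% response to the three quarters of patients not cured by surgery: "We thus estimate the CR rate of neoadjuvant pembrolizumab to be 81"%. For 80% power at an alpha of 0.05 the section gives 9 patients per arm and calls this consistent with 20 patients in total.

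The end of 8.1.4 concludes that 10 per arm is justified for the goals of the study. Neither 8.1.2 nor 8.1.3 names a formula, a test or the sidedness.

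**The concern.** The two sections deal with the same comparison, control rate, alpha and power, and they use the same term for the effect. One needs 40 patients and the other says 20 are adequate. Both can be true only if the term means two different effects, and the sentence in 8.1.3 does not say so. The 81% is an expected rate; the protocol does not present it as a threshold of clinical importance. The only effect it sizes a study for under the label of clinical significance, apart from that projection, is 66% vs 25%.

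What is at stake is how the cure result is read. A reader who takes 8.1.3 at its word could treat a non-significant difference as evidence against pembrolizumab, although a true effect of 66% vs 25% would be missed about half the time or more.

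**Working it through.** **Inputs.** Control cure 25% (8.1.2 and 8.1.3). Treated cure 66% (8.1.2) or 25% + 75% × 75% = 81.25%, given as 81% (8.1.3). Alpha 0.05, power 80%, 10 per arm. Two-sided testing is an assumption.

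**Step 1: reproduce the stated sizes.** Unpooled normal approximation without continuity correction:

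n per arm = (1.960 + 0.842)² × [p1(1−p1) + p2(1−p2)] / (p2−p1)², where (1.960 + 0.842)² = 7.849.

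- 66% vs 25%: 7.849 × (0.1875 + 0.2244) / 0.41² = 7.849 × 0.4119 / 0.1681 = 19.2, so 20 per arm and 40 in total. This matches 8.1.2.
- 81% vs 25%: 7.849 × (0.1875 + 0.1539) / 0.56² = 7.849 × 0.3414 / 0.3136 = 8.5, so 9 per arm. This matches 8.1.3. With 81.25% the result is 8.4, again 9.

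Other variants do not return both figures (per arm, 66% then 81%):

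| Variant | 66% vs 25% | 81% vs 25% |
|---|---|---|
| Pooled, two-sided | 22 | 12 |
| Pooled with continuity correction, two-sided | 27 | 15 |
| Arcsine, two-sided | 22 | 12 |
| Pooled, one-sided | 18 | 9 |
| Arcsine, one-sided | 18 | 9 |
| Unpooled, one-sided | 16 | 7 |

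The unpooled two-sided formula is therefore the likely source of both figures, but this is an inference.

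**Step 2: power at 10 per arm for 66% vs 25%, same formula.**

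Standard error = √(0.4119 / 10) = 0.203. Then 0.41 / 0.203 − 1.960 = 0.060, and Φ(0.060) = 0.524.

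**Step 3: power at 10 per arm for 81.25% vs 25%, same formula.**

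Standard error = √((0.1875 + 0.1523) / 10) = 0.184. Then 0.5625 / 0.184 − 1.960 = 1.09, and Φ(1.09) = 0.862.

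**Step 4: the same two effects under other two-sided methods.** The exact rows sum the probabilities of all 11 × 11 possible outcomes that reach p ≤ 0.05.

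| Method, 10 per arm | 66% vs 25% | 81.25% vs 25% |
|---|---|---|
| Unpooled formula | 52.4% | 86.2% |
| Arcsine formula | 47.6% | 76.4% |
| Pooled formula | 44.8% | 75.1% |
| Pooled z test, exact enumeration | 43.9% | 74.2% |
| Fisher's exact test, exact enumeration | 26.0% | 55.6% |

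If testing were one-sided, power for 66% vs 25% would be 58.5% (pooled), 60.0% (arcsine) or 64.6% (unpooled). No variant reaches 80%.

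**Step 5: the treated rate that 10 per arm detects with 80% power.** About 78% by the unpooled formula, about 84% with a pooled z test, and about 92% with Fisher's test. Even the projected 81% reaches 80% power only under the unpooled formula among the two-sided methods.

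**The case against.** The strongest defence is that 8.1.3 hides nothing. It states the 81%, shows how it is built, says that the 75% comes from drug-resistant metastatic disease, and gives the resulting number per arm. It speaks of a clinically significant difference, not of the one in 8.1.2, and 81% vs 25% would certainly qualify. The 66% in 8.1.2 is there to judge whether a later trial could recruit, and nothing calls it the minimum important difference. Section 8.1.3 also says that no formal calculation was made for this comparison. Cure is a secondary endpoint, 8.3.3 names no between-arm test, and the 20 patients also rest on 8.1.1, 8.1.2 and 8.1.4.

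All of that stands, and it lowers the weight of the point. It does not rescue the sentence: a general claim of adequate power is made, and it fails for an effect that the preceding section calls clinically significant.

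Some stronger readings are tempting but not supported:

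- *The sample sizes are miscalculated.* They are not; both reproduce.
- *The 81% collapses because section 1.2.3 says "Complete responses occur in ~70% of anti-PD1 treated patients".* Sections 1.1 and 1.3.2 give about 75%, in agreement with 8.1.3. With 70% the treated rate is 25% + 75% × 70% = 77.5%, and unpooled power at 10 per arm is 78.8%, only about one point short of 80%.
- *The 75% comes from repeated dosing and so cannot apply to one dose.* Section 1.4.2 describes standard dosing, but the protocol does not say how the patients behind the 75% were dosed.
- *The remark in 1.1 that "This could directly set a new standard of care or motivate a larger, definitive study" must go.* It is aspirational background and makes no power claim.

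**Conclusion.** The point holds as a matter of consistency and wording. The adequate-power statement is supported only for 81% vs 25%. For 66% vs 25% the trial has half the patients that 8.1.2 requires, and two-sided power is between 26% (Fisher) and 52% (unpooled formula), with about 44% for a pooled z test. The range reflects the unnamed test; the conclusion does not depend on which method is chosen, because none reaches 80%. It rests on the protocol's own control rate of 25% and on 10 evaluable patients per arm.

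A reader might infer that the trial is too small for its purpose. The protocol does not support that: the primary endpoints are feasibility proportions, analysed descriptively, and do not depend on this sentence. The correction is worth making, but it is not a condition for the trial to proceed.

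**What to change.** In 8.1.3, replace the adequate-power sentence with text to this effect: *The figure of 9 per arm applies only to the projected cure rates of 81% vs 25%, for which 10 per arm gives power of about 86% by the unpooled formula, 74–75% with a pooled test and 56% with Fisher's exact test. For the 66% vs 25% difference in section 8.1.2, power at 10 per arm is about 26–52% depending on the test. The between-arm comparison of cure is exploratory, and a non-significant result is not evidence of no benefit.* The formula and sidedness behind the stated sizes should be named in the same place.

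It would not be enough to say that a cure rate of 78% is detectable with 80% power, since that holds only under the unpooled formula.

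The cost is a protocol wording change and a less favourable stated power. No patients are added and the design is unchanged.

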1.4.2 Pembrolizumab delivery with respect to second evacuation

As a standard of care, pembrolizumab is given at a flat dose of 200 mg IV once every 3 weeks or 400 mg once every 6 weeks. Usually, patients are commenced on 200 mg before switching to the higher dose once established. Although recent data suggest there is no difference in toxicity between the two regimens³⁵, we propose to offer the lower dose as a precaution.

In the intervention arm, we propose to carry out second evacuation 14 days following a single dose of pembrolizumab. We will allow a 2-day margin either side of the target to accommodate surgical theatre availability. To determine the number of doses and time to second evacuation, we have primarily aimed to balance two competing factors. Firstly, since patients have already been determined to require treatment for disease recurrence, the time between randomisation and evacuation should be minimised to reduce the risk of complications such as vaginal bleeding. Secondly, a period of time is required for maximal pembrolizumab effect in the tumour environment. In deciding on 14 days between pembrolizumab treatment and evacuation, we have considered data from patients with lung cancer treated with a single dose of pembrolizumab, which has shown a maximal effect on circulating T cell activation between 2-3 weeks post dose. In patients with advanced disease, 14 days is considered the minimal time period before a tumour response is seen with hCG decline. Thus a 14 day window ensures sufficient time for pembrolizumab effect whilst minimising the risks associated with tumour progression if therapy is ineffective.

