6.4 Dosage, Duration and Compliance

A single 200 mg IV dose of pembrolizumab will be administered in the treatment arm.

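### The claim in section 8.1.3 that 10 patients per arm give adequate power rests on an 81% cure rate extrapolated from another disease setting, and it fails on the protocol's own alternative figures

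*Protocol*

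**What the plan says.** Section 8.1.3 says that no sample size calculation was made for the comparison of the arms, then asserts that power is nevertheless adequate for a clinically significant difference. Its steps are:

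- Control: "Second evacuation for disease recurrence has a complete response (CR) rate of ~25% based on a study done at our centre".
- Effect of the drug: "Amongst the remainder who relapse, we estimate a 75% CR rate to pembrolizumab based on multicentre data on patients with drug resistant, metastatic disease".
- Combined rate in the pembrolizumab arm: 0.25 + (1 − 0.25) × 0.75, given as 81%.
- Size: "For 80% power with α of 0.05, 9 patients per arm are required".
- Link to the trial's size: "This is consistent with 20 patients in total, randomised 1:1 to the control and neoadjuvant pembrolizumab arms".

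The regimen is fixed in section 6.4: "A single 200 mg IV dose of pembrolizumab will be administered in the treatment arm". Evacuation follows 14 days later (sections 1.4.2 and 3.1). The patients have untreated low-risk disease, no metastases on chest X-ray and hCG under 20,000 IU/L (section 4.1).

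**The concern.** The 75% was observed in drug-resistant, metastatic disease. It enters the formula unchanged for a different population and a different use of the drug. No response rate is given for a single dose before evacuation, and section 1.2 says that immunotherapy before surgery has not been tested in this disease. Section 8.1.3 shows no range around the 81%.

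Two other places in the protocol give less favourable figures. Section 1.2.3 puts complete response to anti-PD1 treatment at about 70%, citing the reference that section 1.1 cites for about 75%. Section 8.1.2 uses 66% versus 25% for the same comparison, calls it conservative and clinically significant, and needs 40 patients to show it. So 8.1.2 asks for 40 patients to detect a clinically significant benefit, and 8.1.3 says that 20 have adequate power for one.

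What is at stake is how the cure result will be read. Section 1.1 says that this trial could itself set a new standard of care or lead to a larger study, and 8.1.3 recalls a four-patient series that changed guidelines. If readers believe that power was adequate, they could take an unremarkable cure difference as evidence against the approach.

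**Working it through.** **Inputs.** Control rate p1 = 0.25, 80% power and α = 0.05 (8.1.3; sidedness is not stated, two-sided assumed). Response x among patients whom evacuation would not cure: 0.75 (8.1.3) or 0.70 (1.2.3). Cure rate of 66% stated directly in 8.1.2. Ten patients per arm (3.2).

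**Step 1: reproduce the plan's figures.** Arm rate p2 = 0.25 + 0.75x. With x = 0.75, p2 = 0.8125. The two-sided normal formula with unpooled variance is

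n per arm = (1.960 + 0.842)² × [p1(1−p1) + p2(1−p2)] / (p2−p1)²

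- 81.25% vs 25%: 7.849 × (0.1875 + 0.1523) / 0.5625² = 8.43, so 9 per arm, as stated.
- 66% vs 25%: 7.849 × (0.1875 + 0.2244) / 0.41² = 19.23, so 20 per arm and 40 in total, as 8.1.2 states.

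The same formula gives both figures. The arithmetic is sound; the question is the input.

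**Step 2: put in the protocol's other response figure.** With x = 0.70, p2 = 0.25 + 0.75 × 0.70 = 0.775, and n = 7.849 × (0.1875 + 0.1744) / 0.525² = 10.3, so 11 per arm.

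**Step 3: power at 10 per arm.** Unpooled: Φ{(p2−p1) / √([p1(1−p1) + p2(1−p2)]/10) − 1.96}.

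- 81.25%: 0.5625 / 0.1843 − 1.96 = 1.09, power 86%.
- 77.5%: 0.525 / 0.1902 − 1.96 = 0.80, power 79%.
- 66%: 0.41 / 0.2030 − 1.96 = 0.06, power 52%.

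The result depends on the test. The pooled z test uses the common variance under the null, with p̄ = (p1+p2)/2: Φ{[(p2−p1)√10 − 1.96√(2p̄(1−p̄))] / √(p1(1−p1)+p2(1−p2))}. Fisher's power is the sum of binomial probabilities over all tables with two-sided p ≤ 0.05.

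| Cure in pembrolizumab arm | Source | n per arm, unpooled | Power at 10 per arm: unpooled z | Pooled z | Fisher, two-sided |
|---|---|---|---|---|---|
| 66% | 8.1.2 | 20 | 52% | 45% | 26% |
| 77.5% | x = 0.70 from 1.2.3 | 11 | 79% | 68% | 47% |
| 81.25% | 8.1.3 | 9 | 86% | 75% | 56% |
| 85% | assumption, x = 0.80 | 7 | 92% | 82% | 64% |

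The last row is an assumption. It shows what follows if untreated low-risk disease responds better than resistant disease.

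**Step 4: how much room there is.** By the unpooled formula, 80% power at 10 per arm needs x of about 0.71 or more, so even 0.70 falls just short. By the pooled z test, 81.25% itself needs 12 per arm. By Fisher's test, power at 81.25% is 74% with 12 per arm and 81% with 13.

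**The case against.** The strongest reply has four parts.

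1. **Direction.** A reader might infer that the 75% comes from repeated dosing, that one dose must do less, and hence that 81% is too high and 9 per arm is wrong. The documents do not support that. Section 8.1.3 gives no schedule for the 75%. Repeat dosing can only be inferred: section 1.4.2 says that in standard care "pembrolizumab is given at a flat dose of 200 mg IV once every 3 weeks" or less often at a higher dose, and 1.4.1 mentions a patient who stopped treatment in an advanced-disease cohort that is not identified as the source of the 75%. Section 1.4.2 says that "14 days is considered the minimal time period before a tumour response is seen with hCG decline", but not that drug effect ends at evacuation, and the endpoint runs to 1 year. It also cites single-dose data on T-cell activation in lung cancer. Untreated, low-risk disease followed by surgical removal could respond better than resistant metastatic disease. This part stands: the 81% is unsupported, not disproved, and any range must extend above it.

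2. **A lower scenario is already present.** Section 8.1.2 plans the definitive study on 66%. That is true, and to the protocol's credit. But the 66% follows the cure rate with single-agent chemotherapy, not a single-dose response, and it is not carried into 8.1.3. Its presence exposes the adequacy claim rather than supporting it.

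3. **The calculation is disclaimed.** Section 8.1.3 says that no sample size calculation was made for this comparison. The same sentence asserts adequate power, a calculation follows, and it is then offered as consistent with 20 patients. The disclaimer softens the point but does not remove it.

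4. **Consequence.** Cure is a secondary endpoint (2.2), the primary analysis is descriptive (8.3.2), and 8.3.3 names no test between arms. A reader might infer that the trial is too small for its purpose. It is not shown to be: section 8.1 also justifies 20 patients by precision for completion and recruitment and by the translational calculation. This part stands and limits the severity.

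**Conclusion.** The concern holds as a correction to a stated power. The 9 per arm is arithmetically right for 81% versus 25% by the unpooled two-sided formula. However, the 81% is extrapolated from drug-resistant, metastatic disease to one dose with early evacuation in untreated low-risk disease, in a direction that the protocol cannot determine.

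The claim of adequate power does not survive the protocol's own figures. At 10 per arm, power is 79% if response is about 70% and about 52% for the 66% that the protocol itself calls a clinically significant benefit. Both are lower under a pooled or exact test. Even at 81%, power runs from 86% to 56% depending on the test.

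These figures assume a 25% control rate, two-sided α of 0.05 and all 10 patients per arm evaluable. The severity is minor: no primary conclusion and no sample size depends on it.

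**What to change.** In section 8.1.3:

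- Say that the 75% is extrapolated from drug-resistant, metastatic disease and that no rate is available for a single dose before evacuation.
- Withdraw the claim of adequate power and the requirement of 9 per arm as reasons for 20 patients. Let the size rest on feasibility precision and the translational aims.
- Name the test to be used and report its power at 10 per arm over a range of cure rates that includes 66%, 77.5% and 81% and goes above 81%.
- State that a non-significant cure difference will not be read as lack of effect.

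Dose, schedule, design and sample size are unchanged. The cost is a short protocol amendment and a less favourable stated power.

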1. BACKGROUND

1.1 Introduction:

Gestational trophoblastic diseases (GTD) are a variety of rare, pregnancy-related proliferative disorders of placental trophoblasts. GTD ranges from premalignant conditions of partial and complete hydatidiform mole (CHM) to malignant gestational trophoblastic neoplasias (GTN) including invasive mole, choriocarcinoma and the rare placental-site trophoblastic and epithelioid trophoblastic tumours¹.

Patients with GTD are registered at one of three UK centres, of which the largest is Charing Cross Hospital (CXH), London. The CXH Trophoblastic Disease Centre is furthermore the largest of its kind globally with over 1200 registrations per year.

Most patients with GTD are radiologically diagnosed with premalignant hydatidiform mole during early pregnancy and subsequently undergo surgical evacuation of the uterus. Amongst patients with CHM, approximately 15% are not cured by primary evacuation. This is diagnosed usually with rising or plateaued human chorionic gondadotrophin (hCG) levels (a sensitive marker of disease burden)². Patients usually have intrauterine and sometimes extrauterine disease. Postmolar disease at this point is considered to be malignant GTN and requires further therapy, usually with chemotherapy or second evacuation. Chemotherapy carries a number of short and long term toxicities that negatively impact quality of life. Our patient representatives indicate that our predominantly young cohort of women are keen to avoid these toxicities. Approximately one third of patients are cured with second evacuation alone³.

Immunotherapy with pembrolizumab that targets the T cell inhibitory receptor PD1 are highly effective in GTN (~75% cure rate)⁴. In other cancer types that are less sensitive, pembrolizumab delivered prior to disease resection has proven to be highly effective, resulting in high pathological complete response rates (elimination of all viable cancer cells)^{5,6}. These observations motivates us to ask whether treatment with pembrolizumab prior to second evacuation of postmolar GTN could enhance the surgical cure rate and represent a powerful approach to cure this disease without requiring chemotherapy.

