
1.3.2 GTN as an extreme model of tumour rejection triggered by pembrolizumab: how does immunotherapy work?

Across cancer types, it remains unknown why some but not all patients respond to immunotherapy. An essential piece of missing information is precisely how agents such as pembrolizumab work, and in which immune cell population this drug acts on.

T cells are broadly divided into CD4 T helper (Th) and CD8 T cytotoxic cells. These populations recognise antigens presented on MHC class I and class II respectively.

Whilst relatively understudied, Th cells are central to the anti-tumour immune response. This population can adopt a variety of fates to play an important role in recruiting, activating and sustaining the activity of anti-cancer CD8 cytotoxic T cells. Th cells can additionally mediate tumour rejection both directly and indirectly.

In parallel to employing strong mechanisms to prevent immune rejection, GTN is the most immunotherapy responsive cancer type described to date with a cure rate of ~75%. This contrasts with 5 year survival rates of ~40% with the anti-PD1 directed agent nivolumab in advanced melanoma³³ and ~30% with pembrolizumab in lung cancer respectively³⁴. Notably, like many cancer types, GTN has suppressed or absent expression of MHC I required for CD8 T cell recognition, indicating a potentially important but unknown role of Th cells. This disease thus offers a unique opportunity to better understand the mechanisms of immune rejection triggered by anti-PD1 immunotherapy and in particular the CD4 T cell contribution to this. By studying the optimally activated intratumour immune response amongst patients with GTN treated with pembrolizumab in the intervention arm, we expect to greatly advance our understanding of how pembrolizumab acts, which are the effector populations and how they are regulated.

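### Section 8.1.3 rests its 9 per arm on a 75% complete response rate to pembrolizumab where section 1.2.3 gives about 70%; at 70% the same formula needs 11 per arm, and the planned 10 give about 79% power

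*Protocol*

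**What the plan says.** Protocol section 8.1.3 argues that even this small trial could detect a clinically important difference between the arms. Three statements carry the argument:

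- Control arm: "Second evacuation for disease recurrence has a complete response (CR) rate of ~25% based on a study done at our centre".
- Pembrolizumab, applied to the patients whom evacuation alone does not cure: "we estimate a 75% CR rate to pembrolizumab based on multicentre data", which come from patients with metastatic disease resistant to drugs. No reference is attached.
- Result: a CR rate of 81% with neoadjuvant pembrolizumab, and "For 80% power with α of 0.05, 9 patients per arm are required". This is then described as in line with 20 patients randomised 1:1.

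The background gives the activity of the drug in three places:

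- Section 1.2.3, citing reference 4: "Complete responses occur in ~70% of anti-PD1 treated patients".
- Section 1.1, also citing reference 4: "highly effective in GTN (~75% cure rate".
- Section 1.3.2, without a reference: "GTN is the most immunotherapy responsive cancer type described to date with a cure rate of ~75" per cent.

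The title of reference 4 in section 12 calls it a multicentre study of pembrolizumab in drug-resistant GTN.

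**The concern.** Section 8.1.3 says that its input is a CR rate. Outside that section, the only CR rate that the protocol gives for this treatment is the one in 1.2.3, about 70%. The two figures near 75% in the background are described as cure rates. One source, reference 4, is therefore reported in two ways: about 70% complete responses in 1.2.3 and about 75% cures in 1.1. Section 8.1.3 uses the higher value and does not mention the lower one.

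What depends on this is the stated number per arm and the claim of sufficient power for the comparison of cure rates. Section 1.1 says that the trial might by itself change the standard of care, so a reader may lean on that claim when the 20-patient comparison is reported.

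**Working it through.** **Inputs.** Control CR rate 25%, pembrolizumab CR rate r = 75%, alpha 0.05, power 80%, 1:1 allocation (all 8.1.3); alternative r = 70% (1.2.3). Neither the sidedness nor the test is stated.

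**Step 1: find the formula behind the stated figures.** For two proportions, normal approximation, unpooled variance, two-sided alpha 0.05 and no continuity correction:

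n per arm = (1.960 + 0.842)² × [p1(1 − p1) + p2(1 − p2)] / (p1 − p2)², where the first factor is 7.849 before rounding of the two z-values.

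- Section 8.1.3: p1 = 0.25, p2 = 0.25 + 0.75 × 0.75 = 0.8125. n = 7.849 × (0.1875 + 0.1523) / 0.5625² = 8.43, so 9 per arm. This is the protocol's figure.
- Section 8.1.2: p1 = 0.25, p2 = 0.66. n = 7.849 × (0.1875 + 0.2244) / 0.41² = 19.23, so 20 per arm and 40 in total. This too is the protocol's figure.

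A one-sided pooled formula also gives 9 for 8.1.3, but it gives 36 in total for 8.1.2. The two-sided unpooled formula is the one tried that reproduces both.

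**Step 2: change only r to 70%.** p2 = 0.25 + 0.75 × 0.70 = 0.775. n = 7.849 × (0.1875 + 0.1744) / 0.525² = 10.30, so 11 per arm and 22 in total.

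**Step 3: power by the same formula.** Power = Φ(|p1 − p2| / √{[p1(1 − p1) + p2(1 − p2)] / n} − 1.960). For r = 70% and n = 10 this is Φ(0.525 / 0.1902 − 1.960) = Φ(0.80) = 78.8%.

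| r | p2 | n per arm | Power, 9 per arm | Power, 10 per arm |
|---|---|---|---|---|
| 70% | 77.5% | 10.30 → 11 | 74.5% | 78.8% |
| 71% | 78.25% | 9.90 → 10 | 76.2% | 80.4% |
| 73% | 79.75% | 9.14 → 10 | 79.4% | 83.4% |
| 74% | 80.5% | 8.78 → 9 | 81.0% | 84.9% |
| 75% | 81.25% | 8.43 → 9 | 82.5% | 86.2% |

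**Step 4: thresholds.** At r = 73.5%, n = 8.96, so 9 per arm needs a rate of about 73.5% or more. Ten per arm is enough from about 70.8%.

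**Step 5: sensitivity to the formula.**

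- Pooled, two-sided: 12 per arm at 75% and 13 at 70%. Power at 10 per arm is 75.1% and 67.6%.
- Fisher's exact test, two-sided: power at 10 per arm is 55.6% at 75% and 47.3% at 70%.
- Pooled, one-sided (the other reading that gives 9): 11 per arm at 70%, the same answer as in Step 2.

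**The case against.** The strongest reply is that 8.1.3 contains no arithmetic error. From its stated inputs, 81% and 9 per arm are correct. The value 75% appears in three places and about 70% in only one, so the slip may lie in 1.2.3. This stands to the extent that the protocol cannot settle which figure is right. It does not remove the inconsistency, because two of those three mentions are cure rates and 8.1.3 says that it uses a CR rate.

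A reader might infer that 1.1 must be wrong because cures cannot exceed complete responses in one series. The text does not support that. Both background figures are approximate, and a rate of 72–73% could be rounded either way. Section 1.2.3 also speaks of patients given anti-PD1 treatment and 1.1 of pembrolizumab, so the denominators may differ. Nor is the 70% the centre's own result: reference 4 is multicentre, and the only own-centre input in 8.1.3 is the 25%.

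A reader might also infer that the trial of 20 is too small once 70% is used. That goes too far. At exactly 70% the shortfall is one patient per arm and 1.2 points of power, and about 71% removes it. Section 8.1.3 also says that no sample size calculation was made for this comparison. The size rests as well on treatment feasibility (8.1.1), recruitment (8.1.2) and the translational estimate of 9 per group (8.1.4). Surgical cure is a secondary endpoint, section 8.3.3 states no test between the arms, and 8.1.2 already shows a more cautious scenario of 66% against 25% with 40 patients. All of this stands and keeps the point minor.

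Finally, the choice of formula moves the power more than the choice between 70% and 75%. That is true, and the correction should therefore cover the formula too.

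**Conclusion.** The point holds in a limited form. The protocol gives two values for the response rate behind its power statement and does not reconcile them. The unqualified 9 per arm depends on the higher one and fails below about 73.5%. At 70% the requirement is 11 per arm, with power of 74.5% at 9 and 78.8% at the planned 10, where the protocol's inputs imply 86.2%. The total of 20 is barely affected.

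These figures assume two-sided alpha 0.05, unpooled variance, 1:1 allocation, a 25% control rate and no dropout. The formula is inferred because it reproduces both 9 per arm and 40 in total. It is the most favourable of the two-sided methods tried; an exact test gives roughly 47–56% power at 10 per arm over the same range. The protocol supports neither the conclusion that 75% is wrong nor the conclusion that the sample size must change. Severity is minor.

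**What to change.** 1. Check the pembrolizumab response figure against reference 4 and use it consistently in 1.1, 1.2.3, 1.3.2 and 8.1.3, stating each time whether it is a complete response rate or a cure rate. Cite the source in 8.1.3.
2. Name in 8.1.3 the formula or test and the sidedness of alpha.
3. Replace the unqualified 9 per arm with the power that 10 per arm gives over the range. Suggested wording: With 10 patients per arm and a control rate of 25%, power is about 79% if the response rate to pembrolizumab is 70% (77.5% against 25%) and about 86% if it is 75% (81% against 25%), by a two-sided normal approximation with unpooled variance. This approximation is favourable at this sample size; Fisher's exact test gives about 47% and 56%.

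The cost is a change of protocol wording and a less favourable power statement. Enrolment, endpoints and planned analyses stay as they are.
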